TITLE: EFFECTIVENESS OF PREHABILITATION ON PELVIC FLOOR WEAKNESS, FUNCTIONAL PERFORMANCE AND RECOVERY EFFICIENCY AMONG POST SURGICAL CERVICAL CANCER WOMEN

NCT: Not yet assigned

Unique Protocol Id: 063/05/2025/ISRB/PGSR/SCPT

Document Date: 2025.05.09

Subjects: Patients with cervical cancer undergoing radical hysterectomy.

Sampling technique: Simple random sampling technique.

Sample size: 34

Selection criteria

The selection criteria for the present study were carefully formulated to ensure the inclusion of participants who could safely undergo the intervention and provide reliable outcome data, while excluding individuals with conditions that could confound the results or pose medical risks. The criteria were applied uniformly during participant screening prior to enrollment.

Inclusion Criteria

Women aged between 40 and 60 years

Confirmed diagnosis of cervical cancer

Preoperative diagnosis of early-stage cervical cancer

Planned to undergo radical hysterectomy

Karnofsky Performance Scale score between 50 and 70

Ability to actively engage in pelvic floor and resistance training protocols

Willingness to participate in the study

Provision of written informed consent prior to inclusion

Exclusion Criteria

Diagnosis of locally advanced or metastatic cervical cancer

Presence of cardiopulmonary comorbidities limiting exercise tolerance

Active urinary tract infection at the time of assessment

Cognitive impairments interfering with understanding or compliance with intervention

Any medical condition contraindicating participation in structured exercise programs

Study procedure

After obtaining approval from the Institutional Ethics Committee, the study was conducted as a randomized controlled trial among patients diagnosed with cervical cancer and scheduled to undergo radical hysterectomy. The study setting included the inpatient and outpatient departments. Potential participants were screened by the investigator based on the predefined inclusion and exclusion criteria. Eligible participants were approached individually and a detailed explanation of the study objectives, procedures, potential benefits and possible risks was provided in a language understandable to them. Adequate time was given for clarification of doubts following which written informed consent was obtained prior to enrolment in the study.

A total of 34 participants who satisfied the selection criteria were included. Simple random sampling was adopted for participant selection and random allocation into two groups was carried out using the lottery method to ensure unbiased group assignment. The participants were equally divided into two groups, the intervention group and the control group, with 17 participants in each group. Allocation concealment was maintained throughout the recruitment process to minimize selection bias.

Baseline assessments were conducted four weeks prior to the scheduled surgical procedure. Pre-test measurements included assessment of pelvic floor muscle strength using the Brink score, evaluation of overall functional status using the Karnofsky Performance Scale and assessment of recovery efficiency through the anticipated duration of hospital stay. All baseline assessments were performed before the commencement of the exercise intervention to ensure uniformity in data collection.

Participants allocated to the intervention group underwent a structured prehabilitation exercise program for a duration of four weeks prior to surgery. The prehabilitation protocol consisted of three supervised sessions per day, each lasting 20 minutes, amounting to a total of 60 minutes of exercise daily. The first session focused on aerobic training, which included activities such as walking, cycling and treadmill exercises based on the individual's choice, tolerance and fitness level. The second session emphasized pelvic floor muscle strengthening exercises, which were individualized and performed as two sets of ten repetitions to improve pelvic floor muscle activation and endurance. The third session consisted of resistance training exercises targeting both upper and lower limb muscle groups using appropriate equipment also performed as two sets of ten repetitions. Exercise intensity and progression were individualized based on the participant's functional capacity and clinical status.

Participants in the control group received a generalized standard exercise protocol for four weeks prior to surgery. This protocol included free exercises, breathing exercises

and walking, delivered in three daily sessions similar in duration to the intervention group. However, no structured or targeted prehabilitation components such as resistance training or specific pelvic floor muscle strengthening were included in the control protocol.

Following surgery, participants in both groups underwent standardized postoperative rehabilitation for a period of two weeks. Postoperative rehabilitation included breathing exercises, pelvic floor strengthening exercises such as Kegel exercises and pelvic bridging and core strengthening exercises aimed at promoting early mobilization, improving functional recovery and preventing postoperative complications. The postoperative rehabilitation protocol was uniform for both groups to ensure comparability. Post-intervention assessments were conducted as per the study timeline after two weeks to evaluate the effectiveness of the intervention.

Materials Required

The materials required for the study included basic exercise and assessment equipment. For the intervention group, resistance bands, weight cuffs, dumbbells and a Swiss ball were used to perform aerobic, resistance and pelvic floor strengthening exercises. For outcome assessment, a couch and a stopwatch were used to facilitate standardized functional and pelvic floor muscle evaluations.

Outcome measures

To evaluate the effectiveness of the prehabilitation program on functional status, pelvic floor muscle performance, and recovery efficiency, standardized and clinically validated outcome measures were utilized. These measures were selected to comprehensively capture both functional and physiological changes associated with the intervention and to allow objective comparison between the intervention and control groups across the study period.

Brink Score: The Brink Score was used to evaluate pelvic floor muscle strength. The Brink score is a digital vaginal palpation scale used to assess pelvic floor muscle function by evaluating pressure (strength), duration (endurance), and vertical displacement (lift). With the patient in supine or crook-lying position, a gloved finger is inserted vaginally and the patient is instructed to contract the pelvic floor muscles. Each component is scored from 0 to 4, giving a total score of 0–12. Scores of 0–3 indicate severe weakness, 4–6 moderate weakness, 7–9 fair strength and 10–12 strong pelvic floor muscles.

Karnofsky Performance Scale: The Karnofsky Performance Scale (KPS) is a standardized tool used to assess a patient's functional status and ability to perform daily activities, particularly in oncology and chronic illness care. KPS is widely used to evaluate disease severity, prognosis, treatment tolerance, and eligibility for therapies, and to monitor changes in functional capacity over time.

Duration of hospital: The duration of hospital stay was used as a measure of recovery efficiency. It was calculated as the number of days from the date of surgery to the date of hospital discharge, as documented in medical records. Shorter hospital stay was interpreted as improved recovery and functional readiness for discharge.

Data Analysis

The collected data were analyzed using SPSS with a significance level set at $p < 0.05$. Normality of continuous variables was assessed using the Shapiro–Wilk test, which indicated a non-normal distribution of the primary outcome measures, including Brink score and Karnofsky Performance Status (KPS). Due to the non-parametric nature of the data, within-group comparisons of pre and post-intervention scores were performed using the Wilcoxon signed-rank test, which is appropriate for evaluating paired differences in related samples when the assumption of normality is not met. Between-group comparisons at baseline and post-intervention were conducted using the Mann–Whitney U test, a non-parametric alternative to the independent samples t-test, suitable for comparing two independent groups with skewed data. Effect sizes were calculated to determine the clinical significance of observed changes in outcome measures. Recovery efficiency measured as hospital stay duration was summarized using descriptive statistics specifically mean and standard deviation to reflect the overall trend in postoperative recovery between groups. This combination of non-parametric tests and descriptive statistics ensured accurate and robust evaluation of the intervention's impact on pelvic floor strength, functional performance and recovery outcomes among post-surgical cervical cancer women.

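### Recovery efficiency is given a forecast as its baseline but is defined as observed days in hospital; it has no true pre-test value and is compared between arms only descriptively.

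*Combined protocol and SAP*

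**What the plan says.** Study procedure, on timing: "Baseline assessments were conducted four weeks prior to the scheduled surgical procedure". The pre-test set is the Brink score, the Karnofsky scale and "assessment of recovery efficiency through the anticipated duration of hospital stay". All three are to be done before the exercise programme starts. The text does not say who makes the forecast, by what method, or whether that person knows the allocation. The lottery allocation is described before the baseline assessments, but the order of the two events is not fixed.

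Outcome measures, under the entry for hospital duration: "It was calculated as the number of days from the date of surgery to the date of hospital discharge". The source is the medical record.

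Data Analysis gives stay a sentence of its own: "Recovery efficiency measured as hospital stay duration was summarized using descriptive statistics specifically mean and standard deviation", and the stated purpose is "to reflect the overall trend in postoperative recovery between groups". The paired analysis is described separately: "within-group comparisons of pre and post-intervention scores were performed using the Wilcoxon signed-rank test". It follows a sentence that names Brink and Karnofsky as the primary outcome measures. The Mann-Whitney test is planned for between-group comparisons at baseline and after the intervention, without a list of outcomes.

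**The concern.** Brink and Karnofsky are measured twice on the same scale, so a change from pre to post has a meaning. Stay is different. Its pre-test value is somebody's expectation and its post value is a count of days. They share an outcome name but are two quantities, and the outcome as defined has no baseline.

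The label invites a pre/post row for stay beside the other two outcomes. The introduction to Outcome measures speaks of capturing change across the study, and Data Analysis computes effect sizes for changes in outcomes without setting stay aside. A fall from anticipated to actual stay could then be read as better recovery when it shows only that forecasts ran long.

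The second part concerns what is actually planned. Recovery efficiency is one of three outcomes in the trial's title, yet the only analysis specified for it is a mean and standard deviation per group. That gives no estimate of the difference with its uncertainty, and no test.

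**Working it through.** **Step 1: the plan's own figures.** The documents give no anticipated or observed stay, no standard deviation and no expected effect. The only related figure is "Sample size: 34", 17 per arm. It cannot be reproduced, because no effect size, standard deviation or power is stated.

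**Step 2: the two definitions side by side.**

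| | Study procedure | Outcome measures |
|---|---|---|
| Quantity | anticipated stay | observed days, surgery to discharge |
| When known | four weeks before surgery | at discharge |
| Source | not stated | medical records |
| Role | pre-test | outcome |

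**Step 3: what each contrast estimates.** Let mean observed stay be m in the control arm and m + t in the intervention arm, where t is the treatment effect. Let mean forecast be m + b(C) in the control arm and m + b(T) in the intervention arm.

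- Change within the intervention arm: (m + t) - (m + b(T)) = t - b(T).
- Change within the control arm: -b(C).
- Between-arm difference in change: t - (b(T) - b(C)).
- Between-arm difference in observed days: t.

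Only the last does not involve the forecast. The difference in change equals t if b(T) = b(C), and otherwise does not.

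**Step 4: numbers, all assumed.** Observed stay has mean 8 and SD 2 days, forecast SD is 1 day, forecasts are equally biased in both arms, and there are 17 per arm. The formulas in step 3 give the following, and a simulation of 20,000 trials agrees to within 0.01 day.

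| Effect t | Forecast bias | Change, intervention arm | Difference in change | Difference in observed days |
|---|---|---|---|---|
| 0 | -2 | +2 | 0 | 0 |
| 0 | 0 | 0 | 0 | 0 |
| 0 | +2 | -2 | 0 | 0 |
| -1 | -2 | +1 | -1 | -1 |
| -1 | 0 | -1 | -1 | -1 |
| -1 | +2 | -3 | -1 | -1 |

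**Step 5: precision.** The standard error of the difference in observed days is sqrt(2 × 4/17) = 0.69. For the difference in change it is sqrt(2 × (4 + 1 - 2 × r × 2 × 1)/17), where r is the correlation of forecast with actual stay. This is sqrt(10/17) = 0.77 at r = 0 and sqrt(6/17) = 0.59 at r = 0.5. Whether subtracting the forecast adds or removes noise therefore depends on a correlation that the documents do not give.

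**Step 6: hypothetical tests.** The plan specifies neither of the first two tests below; they show what a pre/post reading of stay could do. The second set of assumptions is: log-normal stay with mean 7.4 and SD 2.7 days, forecast SD 1 day, no treatment effect.

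- Within-arm Wilcoxon, forecast against actual: significant in 15%, 33% and 76% of trials when forecasts are 0.5, 1 and 2 days too long.
- Mann-Whitney on change: 5%, 17% and 53% when mean forecasts differ between arms by 0, 1 and 2 days.
- Mann-Whitney on observed days, same three gaps: 4.7%, 4.8% and 4.7%, close to the 5% level throughout.

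**Step 7: what a test on observed days could detect.** By the normal approximation for two means, two-sided 5% level and 80% power, the detectable standardised difference is (1.96 + 0.84) × sqrt(2/17) = 0.96. That is about 1.9 days at an assumed SD of 2, or 2.6 days at an SD of 2.7.

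**The case against.** The strongest reply is that the harm belongs to an analysis the plan does not contain. Stay has its own descriptive sentence, directed at a comparison between groups, and the paired test is stated for scores, which in context means Brink and Karnofsky. No change in stay is defined anywhere. That is correct: the planned summary of observed days is untouched by the forecast.

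A reader might go further than the documents allow in four ways:

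- That any pre-to-post summary of stay shows only forecast error. This is too broad. A within-arm change mixes that error with any effect, and equal bias in the two arms cancels from a difference in change.
- That a between-group test would be of no use while the forecast remains. A test on observed days does not use the forecast, and step 6 shows it holding its level.
- That the records-based outcome has lost its meaning. Its definition in Outcome measures stands whatever was forecast.
- That forecasts were made with knowledge of allocation and differed by arm. The text leaves this open but does not show it. Allocation concealment is claimed for recruitment, which does not settle who knew what when the forecast was made.

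What survives the objection is the mismatch between the two sections, the absence of any stated use for the forecast, and the absence of an inferential comparison for stay.

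**Conclusion.** The point holds in this limited form. The mismatch follows from the text alone and needs no assumption: recovery efficiency has a forecast in the place of a baseline and no true pre-test value. The consequence is conditional. If a within-arm change in stay were reported, it would be off by the mean forecast bias, day for day. A between-arm difference in change would be unbiased only if forecasts were equally biased in both arms, and the documents do not secure this because they state neither who forecasts nor whether it precedes allocation.

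Every percentage in the working is hypothetical, since the stay inputs, the forecast errors and the pre/post tests are all assumed. They do not show that this trial's result is biased. The gap that exists without any such assumption is that a titled outcome is compared only by mean and standard deviation. This is an improvement worth making, not a fault that invalidates the trial.

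**What to change.** 1. Remove anticipated stay from the pre-test outcome measurements in Study procedure, and from any pre/post table.
2. Define recovery efficiency once, as observed days from surgery to discharge, and state that it has no baseline value.
3. In Data Analysis, compare observed days between arms with the Mann-Whitney test already used for the other outcomes. Report median, IQR and the Hodges-Lehmann difference with 95% CI alongside the mean and standard deviation. With 17 per arm the interval will be wide and should carry the interpretation; a non-significant result would not show equal recovery.
4. If the forecast is kept, label it a descriptor and state who made it, how and when. Use it as a prognostic covariate only if it was recorded before allocation.

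The cost is one more test and a few lines of text, with no extra patients, visits or staff. The document is written in the past tense and already reports a normality result. If data are in hand, the timing of the forecast can no longer be changed; relabelling and the added comparison remain possible, and the comparison should be reported as an addition to the plan.

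### No masking is stated for whoever scores Brink and KPS, the only outcomes tested between arms, and baseline is not fixed before the lottery draw

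*Combined protocol and SAP*

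**What the plan says.** The Outcome measures section of the combined protocol and SAP describes Brink as a palpation scale in which "a gloved finger is inserted vaginally and the patient is instructed to contract the pelvic floor muscles". Three components are graded 0 to 4, for a total of 0 to 12. KPS is described there as a tool for assessing functional status; no rater is named. The introduction to that section says the three measures together, including hospital stay, were chosen "to allow objective comparison between the intervention and control groups across the study period".

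Study procedure gives two relevant safeguards. On assignment: "Allocation concealment was maintained throughout the recruitment process to minimize selection bias". On baseline timing: "All baseline assessments were performed before the commencement of the exercise intervention to ensure uniformity in data collection". Post-test follows two weeks of postoperative rehabilitation, with no assessor named.

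Data Analysis lists Brink and KPS among the primary outcomes and compares them between arms by Mann-Whitney at baseline and post-test, and within arms by Wilcoxon signed-rank. Hospital stay is only summarised by mean and standard deviation. Blinding or masking is not mentioned anywhere in the document.

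**The concern.** Both tested outcomes depend on a person's judgement. The arms are easy to tell apart before surgery, because only the intervention arm has resistance work and targeted pelvic floor training. Nothing in the text prevents the person who supervised those sessions from later grading the same woman's pelvic floor.

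Concealment protects the assignment and ends once the lot is drawn. Neither randomisation nor a rank test corrects scores that were rated more generously in one arm. If that happened, a significant Mann-Whitney result could be read as an effect of prehabilitation when part or all of it came from the rater. The one outcome taken from records, hospital stay, has no planned test that could support or contradict the rated outcomes.

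The timing rule leaves a second gap. A baseline taken after the draw but before the first session satisfies the plan, so a baseline rating could also be made with the group known.

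**Working it through.** **1. What each safeguard covers**

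| Statement in the plan | Covers | Leaves open |
|---|---|---|
| Lottery allocation, concealed during recruitment | Who enters which arm | Scoring after assignment |
| Baseline before exercise starts | Training effect on baseline | Whether the group is known at baseline |
| Control sessions of similar duration; same postoperative programme in both arms | Contact time; visible activity in the two weeks before post-test | What the rater knows from the four weeks before surgery |
| Post-test after two weeks | Timing | Who scores, and what they know |

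**2. Which analyses each gap reaches**

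- A biased post-test rating affects the post-test Mann-Whitney test and the within-group Wilcoxon tests.
- A biased baseline rating affects the baseline Mann-Whitney test and the Wilcoxon tests. It does not enter the post-test Mann-Whitney test, which uses post-test scores only.
- KPS of 50 to 70 is an inclusion criterion, and Selection criteria says screening preceded enrolment. Some KPS rating must therefore predate enrolment. The baseline gap applies to Brink, and to KPS only if it was rated again after screening.

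**3. How sensitive the post-test comparison is**

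From the document: "Sample size: 34", "with 17 participants in each group", significance level 0.05. The level is taken as two-sided, because sidedness is not stated. The document gives no SD, effect size or power, so 34 cannot be reproduced, and every other input below is an assumption.

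Model for Brink: normal with mean 7 and the SD shown, rounded and limited to 0 to 12. There is no true effect, and one point is added for a share of intervention women. The test is a tie-corrected asymptotic Mann-Whitney, with 6,000 simulated trials per cell. Entries are the percentage with p < 0.05.

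| Assumed SD | No shift | Half shifted | All shifted |
|---|---|---|---|
| 1.5 | 4.6 | 13.6 | 44.3 |
| 2.0 | 4.7 | 10.3 | 26.9 |
| 2.5 | 4.5 | 8.3 | 19.0 |

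A separate run of 20,000 trials per cell gave 43.0, 26.6 and 18.6 for a full one-point shift.

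A hand check at SD 2, by normal approximation:
- The shift is 1/2 = 0.5 SD, and the standard error is √(2/17) = 0.343 SD.
- 0.5/0.343 = 1.458, and 1.960 − 1.458 = 0.502.
- The upper-tail probability is 0.308, or about 31%. This is close to the 27% for Mann-Whitney on rounded scores.

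For KPS, scored in assumed 10-point steps with one step added for a share of intervention women:

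| Assumed SD | One third shifted | Half shifted |
|---|---|---|
| 8 | 16.2 | 31.5 |
| 10 | 12.1 | 23.7 |
| 12 | 10.4 | 18.2 |

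An SD near 8 is not extreme. Entry scores spread evenly over 50, 60 and 70 have SD √((100 + 0 + 100)/3) = 8.2.

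**The case against.** The strongest reply is that silence is not evidence of unmasked rating, and that several stronger readings go beyond the text.

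- A reader might infer that raters knew the group, or that one person screened, drew lots, supervised and scored. The document assigns only screening, to the investigator. What can be said is that masking is not stated.
- A reader might infer that concealment is the only protection against bias. It is not: there is random allocation, an active control of similar session length, and a uniform postoperative programme that includes Kegel exercises. A stopwatch is listed for outcome assessment, so the duration part of Brink may be timed. None of these masks the rater, and pressure and lift remain judgements.
- A reader might infer that Brink and KPS are themselves called objective. The wording covers all three measures, one of which comes from medical records.
- A reader might infer that late baseline rating undermines the main between-group result. It does not reach the post-test Mann-Whitney test.
- A reader might take 19% to 44% as this trial's error rate. Those figures need a full extra point for every intervention woman and none for any control.
- The document is written in the past tense and reports a normality result, so rating arrangements may no longer be changeable. It also says nothing about staffing.

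All of these limits stand. They narrow the point without removing it: no sentence in the plan addresses how post-test rating is protected.

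**Conclusion.** The concern holds as an omission. The plan leaves differential rating uncontrolled at post-test for both outcomes that it tests between arms. It also leaves open whether baseline Brink, and any repeated KPS, precedes the draw. The post-test gap stands on its own and matters more.

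The size of any bias cannot be derived from the documents. The figures show only that, at 17 per arm, modest shifts in rating are enough to matter: roughly 8% to 44% false positives for Brink and 10% to 32% for KPS across the settings tried, against about 5% with no shift. Means, SDs, step size and shifts are all assumed. Calling Brink and KPS the primary outcomes is a fair reading, although Data Analysis introduces them as included among the primary measures and there could be others.

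**What to change.** 1. In Study procedure, require baseline Brink, and any KPS re-rating after screening, to be recorded before the woman's lot is drawn. This costs a sentence and needs no extra staff.
2. Where existing staffing allows, state that post-test Brink and KPS are scored by someone who did not supervise that woman's pre-surgery sessions and is not told her group. The cost is scheduling effort, and masking may fail if women mention their exercises. If no such person is available, this would need an added assessor, and the documents give no basis for assuming one.
3. If item 2 is not possible, or the data are already collected, describe Brink and KPS as unmasked, assessor-rated outcomes. Restrict the claim of objectivity in Outcome measures to hospital stay from records. Say in the conclusions that a difference in the rated scores may partly reflect rater expectation. This is a change of wording only.

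### The between-group test of post-intervention Brink and KPS ignores the baseline scores already collected: valid, but it may waste power, and the separate baseline test does not deal with chance imbalance at 17 per group

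*Combined protocol and SAP*

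**What the plan says.** Under Study procedure, the baseline assessment takes place four weeks before surgery and before any exercise: "Pre-test measurements included assessment of pelvic floor muscle strength using the Brink score, evaluation of overall functional status using the Karnofsky Performance Scale". Allocation is described as "random allocation into two groups was carried out using the lottery method", "with 17 participants in each group", with no mention of stratifying on either score. Under Inclusion Criteria, eligibility requires a "Karnofsky Performance Scale score between 50 and 70".

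Under Data Analysis, baseline scores are used in two places. The first is inside each group: "within-group comparisons of pre and post-intervention scores were performed using the Wilcoxon signed-rank test". The second is a test of its own: "Between-group comparisons at baseline and post-intervention were conducted using the Mann–Whitney U test". The section also says "Effect sizes were calculated to determine the clinical significance of observed changes in outcome measures", but names no measure. It describes no adjusted model, no between-group test of change, and no step for groups that start unequal.

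**The concern.** The question the trial was randomised to answer is whether the two groups differ after the intervention. On the plan as written, that comparison uses only the post scores. The within-group tests do not compare the randomised groups, and an unnamed effect size cannot be read as a baseline-adjusted contrast.

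Two things are at stake. If women with higher baseline scores also tend to have higher post scores, adjustment removes that part of the variation, and leaving it in costs power that the same 34 women could supply. And if the lottery happens to produce groups with different baseline scores, part of that difference carries into the reported effect. The baseline Mann-Whitney test does not help with the second. With 17 per group a non-significant result is weak evidence of balance, and a significant one leads to no action in the plan.

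**Working it through.** **Inputs from the document.** 17 per group; significance level 0.05 (two-sided assumed, as sidedness is not stated); Brink 0–12; baseline KPS 50–70. The total of 34 comes with no target effect, SD, power or dropout rate, so only 17 + 17 = 34 can be checked.

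**Assumptions.** Pre-post correlation r from 0 to 0.7; true effect 0.8 SD in the main runs; KPS scored in steps of 10.

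**1. Efficiency by formula.** Adjusting for baseline multiplies the residual variance by 1 − r². Thirty-four adjusted women are then worth 34/(1 − r²) unadjusted ones: 34/0.91 = 37 at r = 0.3, 34/0.75 = 45 at 0.5 and 34/0.51 = 67 at 0.7. The effect detectable with 80% power is (1.96 + 0.842) × √(2/17) = 0.96 SD unadjusted. Multiplied by √(1 − r²) it becomes 0.92, 0.83 and 0.69 SD. These are normal approximations that ignore the one degree of freedom spent.

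**2. Efficiency by simulation.** There were 6,000 trials per setting, comparing Mann-Whitney on post scores with rank ANCOVA (ranked post score on group and ranked baseline).
- Brink-like: bivariate normal, baseline mean 5, post mean 6, SD 2, rounded to 0–12.
- KPS-like: latent baseline mean 60, SD 10, rounded to tens and kept only if 50, 60 or 70; post mean 70, latent SD 10, rounded to tens; effect 8 points.

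| r (latent) | Brink: Mann-Whitney | Brink: rank ANCOVA | KPS: Mann-Whitney | KPS: rank ANCOVA |
|---|---|---|---|---|
| 0 | 0.592 | 0.584 | 0.564 | 0.554 |
| 0.2 | 0.600 | 0.603 | 0.574 | 0.573 |
| 0.3 | 0.593 | 0.624 | 0.581 | 0.590 |
| 0.5 | 0.593 | 0.696 | 0.616 | 0.657 |
| 0.7 | 0.576 | 0.810 | 0.661 | 0.786 |

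The KPS columns need care. Restricting baseline lowers the Spearman correlation among eligible women to 0.20, 0.34 and 0.52 at latent r = 0.3, 0.5 and 0.7. It also shrinks the post SD, so 8 points is 0.8 of the latent SD but about 0.85 and 0.91 of the restricted SD at latent r = 0.5 and 0.7. A different KPS-like construction, in which Mann-Whitney power stays near 0.56, gave 0.56 vs 0.64 at r = 0.5 and 0.56 vs 0.76 at 0.7.

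**3. Validity.** With no treatment effect, Mann-Whitney rejected in 4.4–5.5% of trials and rank ANCOVA in 4.6–5.6%. Both hold their level over randomisations.

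**4. Chance imbalance.** The standard error of the baseline mean difference is √(2/17) = 0.343 SD. The baseline difference must therefore exceed about 1.96 × 0.343 = 0.67 SD to reach p < 0.05. The probability of an imbalance above 0.5 SD is 2 × [1 − Φ(0.5/0.343)] = 0.145. In 20,000 simulated trials the baseline Mann-Whitney test was non-significant in 0.667 of those cases. So about 0.145 × 0.667 = 0.097, or one trial in ten, would carry such an imbalance unflagged.

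**5. Effect of a 0.5 SD imbalance.** The expected post difference moves by r × 0.5 SD: 0.15, 0.25 and 0.35 SD at r = 0.3, 0.5 and 0.7. On the normal approximation the test statistic then has mean r × 0.5/0.343 and SD √(1 − r²), which gives conditional type I error of 6.1%, 7.9% and 9.4%. Simulation of the actual tests gave 5.8%, 7.2% and 8.9% for Mann-Whitney and 5.1%, 5.5% and 5.4% for rank ANCOVA. Nearly all the excess lies in the direction of the imbalance.

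**The case against.** The strongest reply is that nothing here is an error. A Mann-Whitney test on ordinal post scores in a 1:1 randomised trial is legitimate and holds its level, so adjustment is an efficiency choice. That stands, and no bias averaged over randomisations is claimed.

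Second, the gain depends on figures the document does not give. About six weeks, an exercise programme and radical hysterectomy separate the two assessments, and baseline KPS is restricted to a narrow band. A low correlation is plausible; at r = 0.3 the gain is about 3 power points for Brink and 1 for KPS. For larger effects it also shrinks when r is 0.5 or less. On the Brink-like scale at r = 0.5, power is 0.78 vs 0.87 at 1.0 SD, 0.90 vs 0.95 at 1.2 SD and 0.99 vs 1.00 at 1.5 SD. This limits the size of the point but does not remove it: at r = 0 adjustment cost at most about one power point.

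Third, the plan never claims that a non-significant baseline test proves balance. That is fair. The criticism is only that the test is the sole between-group use of baseline and leads to nothing.

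Fourth, the conditional error figures describe one chosen imbalance, and larger ones occur in only 14.5% of trials. This is also fair; they illustrate the mechanism and are not the trial's overall error rate.

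Non-normality is not a counter-argument, since neither rank ANCOVA nor a proportional-odds model needs normally distributed scores.

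**Conclusion.** The point holds as an improvement the trial should make, not as a fault that invalidates its test. The planned comparison is valid, given sound randomisation and no selective loss of data. It sets aside information already in hand. On the assumptions above, the cost at 0.8 SD is negligible for r up to 0.2, 1 to 3 power points at 0.3, about 4 to 10 at 0.5 and about 13 to 23 at 0.7. KPS lies at the lower end, and its figures depend on how the restricted baseline is modelled. The structural gap is certain; its size is not, because r is unknown.

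**What to change.** Replace the unadjusted post-score test as the main between-group analysis of Brink and KPS with a comparison adjusted for the same score at baseline:

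- **Test:** rank ANCOVA, regressing the ranked post score on group and ranked baseline.
- **Estimate:** a proportional-odds model with group and baseline score, giving an adjusted odds ratio with 95% confidence interval. As two models are used, state that the rank ANCOVA p-value is the test and the odds ratio is the accompanying estimate.
- **Sensitivity:** keep the post-score Mann-Whitney test.
- **Baseline:** present the values by group descriptively, without p-values.

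Timing matters. The Data Analysis section is in the past tense and already reports a Shapiro–Wilk result, "which indicated a non-normal distribution of the primary outcome measures", so outcomes may have been seen. In that case the Mann-Whitney result should remain the planned analysis, with the adjusted result reported beside it and labelled as added afterwards.

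The cost is one degree of freedom and a little more analysis of data already collected. No further patients or visits are needed.
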